#### 4.2.9.3 Visit 2 (continuation of the treatment, day 29±2)

#### Visit objective:

- Physical examination, blood pressure and heart rate measurement;
- Metabolic parameters of iron (serum ferritin and iron level, transferrin, iron transferrin saturation percentage);

- Complete blood count (hemoglobin level, hematocrit, RBC);
- Hand-out of the patient diary (Appendix16.1) and instructions on its completion;
- Check of a patient diary completion and collection of diaries;
- Accounting and dispensing of the study product;
- Evaluation of compliance;
- Evaluation of the concomitant therapy;
- Adverse events registration.

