#### 5.3.1.1 Terms and volume of data on the excluded subjects

In the case of study discontinuation on the subject's free will, the Investigator should make effort to find out the reason thereof. In the case of study discontinuation due to AEs/SAEs, the subject should be followed-up until the AEs/SAEs are resolved. In case of early study termination by a patient, he/she should visit the study site for early termination procedures (as an unscheduled visit); if the patient refuses to visit the study site, he/she should be contacted by phone with further recording of all available information.

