## 8 Safety evaluation

## 8.1 Methods and periods for registration of safety parameters

Safety evaluation of the study therapy will be performed throughout the study and will be based on detection of any adverse events occurring during the study. The following will be performed:

- Physical examination, including measurement of blood pressure and heart rate, and gastrointestinal disorders identification (at the screening, during the second visit and the final visit).
- Complete blood count (at screening and in 4, 8 and 12 weeks of therapy),
- Blood biochemistry (at screening and after 12 weeks of treatment),
- Clinical urinalysis, pregnancy test (at screening and in 12 weeks).
- Registration of concomitant therapy (during each visit).

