## 9.2 Interim analysis

One formal Interim analysis to assess the primary and secondary endpoints of efficacy is planned when the population of patients with available primary efficacy endpoint data is at least 240 patients (120 patients in each group treatment: the main group is Ferrum Lek® (iron (III) hydroxide polymaltosate) and the reference group MALTOFER® (iron (III) hydroxide polymaltosate). Safety and Efficacy will be assessed for all patients who received at least one dose of the randomized treatment at the time of the interim analysis. Based on the results of the interim analysis of the primary and secondary statistical endpoints of the efficacy and safety of the study Sponsor may decide to stop the study if study endpoints have been met as per protocol based on the results of interim analyses or sample size might be recalculated using results of interim analyses.

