## **9.8** Procedures for clinical trial participants selection with a view to analysis

The following data sets will be used for analysis:

• The intention-to-treat (ITT) population: all randomized subjects who were administered at least one dose of the investigational product or comparator and who have hemoglobin level data both before and after treatment with the investigational product and the reference product.

In accordance with principles of ICH E9 guidelines, the ITT population will be considered to be a population for statistical analysis.

- The per protocol (PP) population: all randomized subjects who have completed participation in the trial in accordance with the protocol (have completed the prescribed period of treatment and follow-up without significant deviations from the protocol).
- The safety population (safety): All randomized subjects who received at least one dose of the study drug/comparator drug and completed at least one safety parameters evaluation visit. Unlike the ITT population, the safety population will be analyzed depending on actually received treatment rather than not only prescribed (in the case of difference detection between the prescribed and received therapies).

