4.3. Study population

4.3.1. Safety population

All randomized subjects who received at least one dose of the investigational medicinal product and completed at least one safety parameters evaluation visit. As distinct from ITT population, the TS population will be analyzed depending on actually received treatment (not only prescribed) (in case of difference between the prescribed and received therapies).

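### The visit condition in the safety population is undefined; read as post-dose, it can leave out dosed patients who have no visit after Day 1, unlike the all-dosed set used at the interim

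*Protocol*

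**What the plan says.** Protocol 9.8 admits to the safety population "All randomized subjects who received at least one dose of the study drug/comparator drug and completed at least one safety parameters evaluation visit", analysed by treatment actually received. SAP 4.3.1 uses the same two-part rule: "All randomized subjects who received at least one dose of the investigational medicinal product and completed at least one safety parameters evaluation visit". Neither document defines a safety evaluation visit or says when it must take place.

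For a patient who leaves early, Protocol 5.3.1.1 asks for an unscheduled site visit with early termination procedures. It then adds that "if the patient refuses to visit the study site, he/she should be contacted by phone with further recording of all available information".

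The interim analysis has no visit condition. Protocol 9.2 states that "Safety and Efficacy will be assessed for all patients who received at least one dose of the randomized treatment" at the time of that analysis, and SAP 11 says the same in substance.

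**The concern.** A safety set is normally everyone who took the drug. A second condition that a patient can fail by leaving early makes membership depend on something that poor tolerability can cause. Gastrointestinal reactions head the side-effect lists for both products (Protocol 2.1.1 and 2.1.2), and individual intolerance is a listed ground for exclusion from the study (5.3.1). Events requiring termination of therapy, and treatment-related digestive complaints, are named safety analyses (4.1, 9.1.4). If the visit must follow dosing, the patients most relevant to those analyses are the ones who could be missing.

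Safety is the stated secondary objective. The trial is open-label, and Protocol 4.10 says the sponsor will know the allocation. If the meaning of the condition is settled only at analysis, it will be settled by people who can see which arm each affected patient was in.

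**Working it through.** The plan gives no figure for this point, so the check is mainly a comparison of texts.

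**1. What could count as the visit?**
- *Screening.* Protocol 8.1 lists safety assessments that include "gastrointestinal disorders identification (at the screening, during the second visit and the final visit". Every randomised patient was screened, so on this reading the condition excludes nobody.
- *Visit 1 (Day 1).* Adverse events are registered and treatment starts (4.2.9.2). This reading also excludes essentially nobody.
- *A visit after dosing.* The first scheduled one is Visit 2, Day 29±2 (4.2.9.3). Only on this reading does the condition do any work.

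**2. Which reading does the drafting favour?** The protocol's ITT definition (9.8) requires hemoglobin both before and after treatment. SAP 4.3.2 replaces this with one completed efficacy evaluation visit. Hemoglobin is measured at screening (Protocol 7.1). If screening counted, the SAP would admit patients with no post-treatment hemoglobin and so contradict the protocol. The two ITT definitions agree only if the visit is post-dose. The safety wording in SAP 4.3.1 follows the same pattern, which supports a post-dose meaning there too. This is an inference; the words are not in the text.

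**3. Who is lost on the post-dose reading?**
- Attends an early termination visit (5.3.1.1) or an unplanned visit (4.2.7): probably kept. Early termination procedures are not itemised in Table 5 or 4.2.9, and nothing states that such a visit qualifies.
- Reached by phone only: unclear. Section 4.2.9.6 calls the Day 98 phone contact a visit, but 5.3.1.1 treats the call as what happens when the patient refuses to visit.
- Dies or is lost before any visit after Day 1: excluded.

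In each case adverse events are recorded from consent onward (8.3.4), so an event can be in the CRF while the patient is outside the set.

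**4. Interim against final.** Interim safety set: at least one dose (Protocol 9.2, SAP 11). Final safety set: at least one dose and one completed visit (Protocol 9.8, SAP 4.3.1). On the post-dose reading, a patient counted at the interim can be absent from the final safety analysis.

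**5. Size, as an illustration only.** Number lost = N × w × f × u.
- N = 336 and w = 0.15 (Protocol 9.3). N × w = 50.4, consistent with 336 − 286 = 50.
- f = share of withdrawals before Visit 2, and u = share of those with no post-dose visit. The documents give neither, so both are assumed. All withdrawals are taken to have had a dose.
- With f = 1/3: 50.4 / 3 = 16.8. Then u = 0 gives 0; u = 1/2 gives 8.4, about 8 (8/336 = 2.4%); u = 1 gives about 17 (17/336 = 5.1%).
- Extremes: 0 (f or u zero) to about 50 (both 1; 50/336 = 14.9%).

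Effect on a rate: (e − k)/(n − k). Assume e = 8 of n = 168 in one arm stop for adverse events (4.8%) and k = 4 of them have no post-dose visit. The reported rate is then (8 − 4)/(168 − 4) = 4/164 = 2.4%.

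**The case against.** The strongest reply is that the text does not require the visit to follow dosing. Protocol 8.1 names screening among the safety assessment periods, and adverse events are registered at Visit 0 and Visit 1. Read literally, every dosed patient qualifies and there is no bias. Even on a post-dose reading, Day 29 is only the first scheduled visit: early leavers are asked to attend, unplanned visits are allowed, patients stopping for adverse events are followed until resolution (5.3.1.1), and deaths are always notified (8.3.8). The protocol's own summaries of earlier studies report no withdrawals on the polymaltose complex in one comparative trial and describe discontinuation as rare (2.3.4.1). The SAP's adverse event table shells show percentages of events, not of patients, so the rates illustrated here are not figures those shells would display.

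Most of this stands. It limits the affected group to patients with no site contact after Day 1 and leaves the number unknown. It does not remove the ambiguity. An inclusive literal reading makes the condition redundant, and it sits badly with the parallel ITT wording. Safety reporting of individual cases does not put those patients into the set-based summaries. The mismatch with the interim definition also remains.

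**Conclusion.** The condition "completed at least one safety parameters evaluation visit" is undefined. On its more natural, post-dose reading it can exclude dosed patients who die, are lost, or are reached only by phone before Visit 2. That exclusion can depend on tolerability, and the final definition differs from the all-dosed set used at the interim. The number affected is unknown and may be zero. The figures above rest on assumed timing and attendance and show direction only.

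Two stronger readings are tempting. A reader might infer that anyone who stops for early intolerance is dropped. The documents do not support that, because they provide for early termination and unplanned visits before Day 29. A reader might also infer that only Visit 4 counts, since it alone is titled for safety evaluation. Protocol 8.1 and SAP 9 place safety assessments at earlier visits as well, so that is not supported either.

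The primary analysis is untouched. This is a low-cost improvement to the safety analysis, not an error that undermines the trial.

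**What to change.** In Protocol 9.8 and SAP 4.3.1, define the safety population as all randomised subjects who received at least one dose, analysed by treatment received, and delete the visit condition. State that adverse events reported by phone or at unscheduled contacts are counted. State in Protocol 9.2 and SAP 11 that the same set applies at the interim and final analyses.

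The cost is about one sentence for the definition in each document, plus a cross-reference. The downside is that a few patients with little or no post-dose laboratory data enter the denominators; the laboratory tables can show the number with data at each visit. If the condition was never meant to exclude anyone, deleting it changes nothing.

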# 10 Description of arrangements for quality control and quality assurance

## **10.1 Trial monitoring and quality control**

Regular visits by a clinical trial specialist (Monitor), on request of the Sponsor and according to SOPs, before initiation, throughout, and upon completion of the trial contribute to a successful trial conduct and accurate data collection, timely detection of errors, proper documenting of the trial process, protection of the subjects' rights, and consistence with the principles of ICH GCP, international and Russian laws.

Routine trial monitoring includes:

- Confirmation for the proper conduct and documenting of the informed consent receipt, screening, and inclusion of the subjects in the trial.
- Verification of the data in CRF and primary medical documents.
- Confirmation for documenting and timely reporting of AEs during the trial;
- Confirmation for compliance of the study site personnel with the requirements for diagnostic and therapeutic procedures stipulated by the protocol;
- Confirmation for documenting the shipments, storage, distribution, and utilization of the study product/comparator drug and trial materials;
- Confirmation for competence of the study site personnel and external laboratories needed for the trial conduct.
- Confirmation for compliance of the diagnostic and laboratory equipment with the safe use requirements during the trial.
- Confirmation for cooperation of the Investigator with the local Ethics Committee regarding the trial safety and introduction of the protocol amendments agreed upon by the Sponsor.

Quality control of the trial results by the Sponsor's authorized persons or representatives who keep a trial electronic database, reveal for any inconsistence, data imputed by error, or missing data during the cross check of all eCRFs. In the case of any questions or necessity of clarification, a special form (a data clarification request) should be forwarded to the Investigator and satisfied in writing during 7 days since the receipt thereof.

In accordance with the requirements of the legislation, the Sponsor or authorized federal authorities have the right to inspect (audit) the logistical support and documentation on the trial. The Investigator is obliged to provide direct access to documents and all relevant information to the authorized persons for the audit or inspection.

### **10.2** Amendments to the protocol

The investigators' signatures on a signature list of the protocol mean a written consent to perform a trial in accordance with this protocol. During the trial, the trial materials may be amended and appended. Such changes and additions are considered to be amendments.

A protocol amendment is a written description of changes or formal clarification of the clinical trial protocol wordings. The amendments may be significant and insignificant. Any protocol amendment, before making effective, must be approved according to the established procedure and SOPs of the Sponsor, than approved by regulatory authorities and signed by the Investigator. Order of the Ministry of Health of Russia On Approval of a Review Procedure of a Message on Necessity to Introduce Amendments to a Protocol of the Clinical Trial of the Drug No. 775 of August 31, 2010 contains a list of significant/insignificant amendments and a procedure of submission thereof for the expert evaluation.

The protocol amendments are significant if they may influence objectives, organization, methods of the trial, statistical methods of data processing, and patients' safety measures during the trial.

The protocol amendments are insignificant if they may not influence the objectives, organization, methods of the trial, statistical methods of data processing, and measures for patients' safety during the trial.

In the case of necessity to introduce changes into this protocol, the Investigator shall submit a message on necessity to introduce amendments to the clinical trial protocol to the Ministry of Health of Russian Federation. The Ministry of Health of Russia shall consider the submitted documents and decide on approval or refusal to the introduction of changes. The protocol amendments must be stored together with the initial protocol version. A title page of the protocol must contain a number and date of the amendments.

### **10.3 Protocol deviations**

Protocol deviation is an unintentional deviation from the approved protocol.

Serious protocol deviation is a deviation, which may, in the opinion of the Investigator or a person assigned by the Investigator, result in withdrawal of the subject from the study or exclusion of his data from bioanalytical and/or statistical parts of the study. The deviations that were no classified as serious shall be considered minor protocol deviations.

Serious deviations from the Protocol should be reported as soon as possible to the Sponsor by the Site staff and/or CRO and Monitor (if he/she is in the Site). The Sponsor may propose to reclassify the protocol deviation (minor into serious and vice versa) based on the conducted evaluation. In such a case, the classification performed by the Sponsor shall prevail and must be communication to CRO together with written rationale.

The Sponsor must be informed of minor protocol deviations within 10 business days but before the start of the next study period or before the start of the bioanalytical/statistical phase.

An exception is represented with minor protocol deviations, which can be included in the draft report on the trial:

- Logistic deviations (deviation in time from the planned blood sampling schedule; follow-up visit which were outside the time limits set up in the Protocol due to a participant's plans/schedule, etc);
- Administrative deviations (e.g. change of the name).

If less than planned number of volunteers is enrolled, the CRO should contact the Sponsor, who may approve using smaller than planned number of volunteers. It is not considered to be a deviation from the Protocol.

Notification and reporting on deviations from the Protocol shall be submitted to the Regulatory authorities and relevant Ethical Committees in compliance with the applicable requirements/instructions/laws.

#### **Procedure for documentation of Protocol deviations**

The Investigator or a person assigned by the Investigator must document and explain any deviation from the approved Protocol. Notification of the Sponsor on a protocol deviation can be verbal in exceptional cases (if immediate action/notification is required), and must be followed with written report (e.g. via e-mail; during updates on the study period process). All Protocol deviations must be described in the final report on the study.

## 11 Description of ethical aspects of the clinical trial

## **11.1 General provisions**

The trial will be performed in accordance with the principles and requirements set forth in the documents:

- Declaration of Helsinki, World Medical Association (adopted at the 18th Assembly of the World Medical Association in Helsinki in June 1964, the latest revision adopted by the 64th Assembly in Fortaleza in October 2013),
- ICH E6 Harmonized Tripartite Guidelines for Good Clinical Practice dated 09.11.2016
- Guideline for Good Clinical Practice of the Eurasian Economic Union (adopted through the decision No. 79 of the Council of Eurasian Economic Commission dated November 3, 2016);
- Federal law dated April 12, 2010 № 61-FZ "On Circulation of Medicines" (as amended);
- Order No. 200n dated April 01, 2016 of the Ministry of Health of the Russian Federation "On Approval of Rules for Good Clinical Practice";
- The national standard of the RF GOST R 52379-2005 "Good Clinical Practice".

The study will be initiated in all research centers only after obtaining a written permission to conduct research and approval of the Ethics Committee of the Ministry of Health of the Russian Federation and Local Ethics Committees and getting the signatures of each party participating in the study in the Clinical Trial Protocol.

Investigators will be familiarized with the study materials in time prior to the study initiation. Investigators' qualification will meet the requirements essential for conducting high-quality clinical trials.

Selection of prospective study participants is carried out on a voluntary basis.

#### **Ethics Committee**

Clinical trial materials (including CRF, materials provided to the patient) will be approved by the Ethics Committee of the Ministry of Health of the RF and Local Ethics Committees prior to the trial start. All the amendments to the Protocol and updated versions of the Patient Information Leaflet will be submitted to the Ethics Committee for approval.

The clinical trial will be performed in accordance with the Protocol approved by The Ethics Council.

## 11.2 The informed consent receipt procedure

Before the inclusion, a subject is provided with written information and verbal clarification on objectives, goals, and methods of the trial, as well as expected benefit and possible risks associated with the participation in the trial. Besides, the subjects must be informed on voluntary nature of the participation in the trial and their rights to refuse to participate at any moment without influence on quality of the provided medical care. While a subject is not obliged to report his/her reasons to terminate his/her participation in the trial, the Investigator should try to find out the reasons without violating the subject's rights. The subject's consent must be obtained before initiation of any of the trial procedures.

Processing of the data gathered during the trial is performed with the maintenance of confidentiality of personal data. The subjects should be made aware of the goals of the planned computed data processing and publication terms (e.g., on medical conferences, in magazine articles, and other publicly open sources), when the data is presented in summary not allowing for the subjects identification.

Subjects should be made aware that the authorized representatives of healthcare authorities and of the Sponsor will have access to their confidential health information for the purpose of monitoring, inspection, and audit. The subjects must receive guarantees of the strict confidentiality and non-disclosure of all personally identifiable information.

Patient Information Sheet with the informed consent form should be filled in in duplicates, signed, and dated by the subject and Investigator in person. One copy of the signed Patient Information Sheet with the Informed Consent Form should be kept in the Investigator's file, the other copy should be given to the subject.

## 11.3 Confidentiality and identification of the trial subjects

Personally identifiable information will be kept confidential in observance of the right to privacy and confidentiality protection according to the applicable laws. Personally identifiable information will be kept confidential and may be disclosed only to the extent required by law. On publication of the trial results, confidentiality of the personally identifiable information will be maintained.

